## 2. Purpose

This SAP outlines all statistical analyses to be performed on data collected in study SCGAM-03, and the resulting output that will be compiled to support the completion of the Clinical Study Report (CSR).

The planned analyses identified in this SAP will be included in regulatory submissions and/or future manuscripts. Exploratory analyses not necessarily identified in this SAP may be performed to support the clinical development program. Any post-hoc or unplanned analyses performed that are not identified in this SAP will be clearly identified in the respective CSR.

The statistical output provided to the medical writer of the CSR will closely follow the ICH guideline for industry on topic E3 (Structure and Content of Clinical Study Reports) to facilitate the subsequent compilation of the CSR.

This statistical output will consist of tables, figures and listings, including

- Tables, figures and listings used or referenced in, or appended to the CSR as detailed in the remainder of this SAP (section 14 of the CSR)
  - Demographic data summary figures and tables
  - Efficacy data summary figures and tables
  - Safety data summary figures and tables
- Listings provided as appendices to the CSR
  - Patient data listings (section 16.2 of the CSR)
  - Individual patient data listings (section 16.4 of the CSR) will be covered by inclusion of SAS datasets into the electronic submission to the authorities

A detailed list of all tables, figures and listings will be supplied in a separate document later when all feedback from authorities will be available.

---

 International Conference on Harmonization. (1996). Structure and Content of Clinical Study Reports. Structure and Content of Clinical Study Reports (Guideline for Industry) (S. 37). London: International Conference on Harmonization.

### 3. Study Objectives and Endpoints

#### 3.1. Study Objectives

##### 3.1.1. Primary Objective

The primary objective of the study is to assess the medium-to-long-term safety and tolerability of *octanorm*.

##### 3.1.2. Secondary Objectives

The secondary objectives of the study are:

- To assess the effect of *octanorm* on quality-of-life (QoL) measures.
- To obtain further data on the efficacy of *octanorm*.

#### 3.2. Study Endpoints (Target Variables)

##### 3.2.1. Primary Target Variables

There is no single primary endpoint in this present extension study. The primary objective is to assess safety and tolerability in medium-to-long-term administration, and this will be assessed by means of the following outcome variables:

- Occurrence of treatment-emergent AEs (TEAEs) throughout the entire treatment period starting with the first infusion of IMP.
- Occurrence of temporally associated TEAEs.
- TEAEs by speed of infusion.
- Local injection-site reactions.
- Vital signs (blood pressure, pulse, body temperature, respiratory rate).
- Physical examination.
- Laboratory parameters (haematology, clinical chemistry and tests for viral safety).

##### 3.2.2. Secondary Target Variables

Secondary assessment criteria will be for quality of life and efficacy:

- QoL assessments using the CHQ-PF50 from parent or guardian of patients <14 years of age and the SF-36 Health Survey in patients ≥14 years of age. Age here refers to the age at enrollment into study SCGAM-01, so that each patient will continue using the same questionnaire as before.
- Total IgG trough levels.
- Occurrence of serious bacterial infections (SBIs) as defined in Section 10.
- The annual rate of all infections of any kind or seriousness.
- Time to resolution of infections.
- Use of antibiotics (number of days and annual rate).
- Missed days from work/school/kindergarten/day care.

## 4. Study Methods

### 4.1. Overall Study Design and Plan

Study SCGAM-03 is designed as a prospective, open-label, non-controlled, single-arm, multicentre phase III safety follow-up study with observation of patients receiving weekly or bi-weekly doses of *octanorm* over a period of up to two years.

The study will be conducted at study sites in the United States that already participated in the SCGAM-01 trial, and at study sites in Canada enrolling 'de novo' patients who are under other SCIG treatment.

Most US patients will migrate directly from the main study to the present extension study. However, some patients are expected to complete the main study before the commencement of the extension study. Therefore, the following rules are instituted:

- a) Patients who complete the main study after the start of the extension study will be required to migrate directly into the extension study, so that treatment with *octanorm* is not interrupted. (For these patients, the screening visit in the extension study will be the same as the final visit in the main study; extension-study screening tests that also constitute main-study tests for that visit do not need to be duplicated.) Use of an IgG product other than *octanorm* between the main and extension studies will disqualify a patient from entry to the extension study.
- b) Patients who completed the main study before the start of this extension study will be allowed to continue IgG treatment with any commercially available SCIG until the time when they can be treated within the extension study. In the intervening interval they must have received the commercially available SCIG at the approximately same dose which the patient had received in study SCGAM-01. (For these patients, the screening visit will be regarded as a fresh start and all screening procedures are to be conducted.)

Each patient will be treated weekly or bi-weekly with *octanorm*, either at the investigation site (on study visit days) or else at home. Patients may remain in the trial until Octanorm becomes commercially available in the USA, the Sponsor decides to terminate the trial, or December 2020 (whichever comes first). A patient may remain in the trial for up to approximately 4.5 years, i.e. receiving a total of approximately 234 Octanorm infusions (or less, if the infusions will be administered bi-weekly) A final examination will be performed 1 week after the last infusion, for both regular and premature termination of the patient's study participation.

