3.2 Overall Study Design and Plan

The study is a prospective, open-label, non-controlled, single-arm, multicenter phase III safety follow-up study with observation of patients receiving weekly (or bi-weekly at double the weekly dose) doses of Octanorm over a period of up to approximately 4.5 years

The study will be conducted at study sites in the United States that already participated in the SCGAM-01 trial.

Only patients who have completed the main study (SCGAM-01) may be enrolled.

Most patients will migrate directly from the main study into the present extension study. However, some patients are expected to complete the main study before the commencement of the extension study.

Eligible patients who have completed the SCGAM-01 study and were treated with any other commercially available SCIG before the start of the SCGAM-03 study (e.g. owing to a delay in local IRB approval for SCGAM-03) are permitted to enter the SCGAM-03 study.

In the intervening interval they must have received the commercially available SCIG at the approximately same dose which the patient had received in study SCGAM-01. For these patients, the screening visit will be regarded as a fresh start and all screening procedures are to be conducted.

The maximum allowed interval without any IgG treatment before the start of treatment in the SCGAM-03 study is approximately 5 weeks.

Each patient will be treated weekly (or bi-weekly at double the weekly dose) with Octanorm, either at the investigation site (on study visit days) or else at home. Thus the maximum number of study infusions of Octanorm may be up to 234 for each patient (or less if treated bi-weekly). A final examination will be performed 1 week after the last infusion, for both regular and premature termination of the patient's study participation.

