## 7. Analysis Populations

The following populations will be considered for the statistical analysis:

The safety analysis set (SAF) consists of all patients who received at least part of one infusion of *octanorm* within this extension study.

The full analysis set (FAS) is defined according to the intention-to-treat principle and consists of all patients of the SAF who satisfy all eligibility criteria and for whom any post screening data in this extension study are available. It is expected that the FAS will coincide with the safety set.

The per-protocol (PP) set consists of all patients of the FAS excluding those with major protocol violations which may have an impact on the analysis of the primary endpoint. This is the set of patients who participated in the study as intended and for whom the primary endpoint can be evaluated as planned.

Only major protocol deviations with the potential to affect the study results significantly or to invalidate the interpretation of the data obtained will lead to exclusion of patients from the PP set; protocol deviations to be considered will include (but will not be limited to):

- Violations of the study entry criteria.
- Administration of any other blood or plasma-derived product or of any other immunoglobulin preparations during the SCGAM-03 study.
- Any prohibited concomitant medication (including long term corticosteroids, daily,  $\geq 0.15$  mg of prednisone or equivalent/kg/day, immunosuppressive and immunomodulatory drugs).
- Failure to attend two scheduled consecutive visits OR three or more scheduled visits during the study for reasons other than clinical reasons.

Analysis of the safety endpoints will be based on the safety set.

Efficacy endpoints will be analysed on basis of the FAS.

Any analysis might be repeated on basis of the PP analysis set if indicated by the data or in case the PP population differs from the FAS by 3 patients or more, to allow for an assessment of the robustness of the results with respect to protocol violations.

The membership of each patient in the respective analysis populations will be determined before the statistical analysis in a data review meeting by a panel consisting of a medical expert from the Sponsor, the clinical study manager, the data manager and the study statistician.

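### SAP 4.1(a) bars one group of bridged patients whom protocol v7 admits, and the FAS and PP definitions leave room for that rule to be applied

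*SAP*

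**What the plan says.** SAP 4.1 divides US patients by when they finished the main study.

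- Rule (a): "Patients who complete the main study after the start of the extension study will be required to migrate directly into the extension study". Using an IgG product other than octanorm in between "will disqualify a patient from entry to the extension study".
- Rule (b) reads: "Patients who completed the main study before the start of this extension study will be allowed to continue IgG treatment with any commercially available SCIG", at about the SCGAM-01 dose.

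Protocol v7, section 3.2, has one rule. Eligible completers who "were treated with any other commercially available SCIG before the start of the SCGAM-03 study" (a local IRB delay is its example) "are permitted to enter the SCGAM-03 study". They must have received about the same dose in between, and section 4.1.2 limits the time without any IgG.

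SAP 4.3, which describes the study population, also accepts a short period on another SCIG and does not mention completion date.

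On analysis sets, SAP 7 builds the FAS from safety-set patients "who satisfy all eligibility criteria and for whom any post screening data in this extension study are available". Among the deviations to be considered for PP exclusion it lists "Violations of the study entry criteria". Efficacy is analysed on the FAS and safety on the safety set.

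**The concern.** The SAP's document history says v2.0 was written to match protocol v7.0 for the US and v5.0 for Canada. On bridging it does not match the US protocol.

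The mismatch matters because FAS and PP membership both turn on eligibility. The SAP does not reproduce the numbered criteria, so 4.1(a) is its only explicit statement that a patient is disqualified from entry. A panel working from the SAP could apply it. Patients whom the protocol admits would then be missing from the SBI, infection, antibiotic, absence, hospitalization and QoL summaries, although they were treated and followed as the protocol intends.

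**Working it through.** **1. The rules side by side (US completers of SCGAM-01)**

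| Patient | SAP 4.1 | Protocol v7 (3.2, 4.1.2) |
|---|---|---|
| Completed after SCGAM-03 started, no other IgG | Admitted, rule (a) | Admitted |
| Completed before SCGAM-03 started, bridged on commercial SCIG at about the same dose | Admitted, rule (b) | Admitted, subject to the limit on IgG-free time |
| Completed after SCGAM-03 started, bridged in the same way | Disqualified, rule (a) | Admitted, subject to the same limit |

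Only the third row differs. The protocol's own example can fall there: a patient may finish SCGAM-01 after SCGAM-03 has opened elsewhere but before the local IRB has approved it. The SAP does not say whether the start of the extension means the whole study or the site, so it does not settle which rule covers that patient.

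**2. Is rule (a) among the protocol's numbered criteria?** No.

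- Section 4.1.1 asks for completion of SCGAM-01 with good tolerance, consent, a negative pregnancy test where relevant, and willingness to comply.
- Section 4.1.2 bars too long a gap without any IgG, recent exposure to blood products (regular IgG treatment is exempt), and planned pregnancy.
- The Study Outline and section 7.3.1.1 give a separate treatment-emergence rule for patients who received another IgG brand between the studies. The protocol therefore expects to enrol them.

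**3. The route to the analysis sets**

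- The safety set has no eligibility condition, so nobody leaves it.
- The FAS is the safety set restricted to patients meeting all eligibility criteria and having post-screening data. This is where rule (a) could act.
- The PP set is drawn from the FAS, so a patient lost from the FAS is lost from both. Such a patient adds 0 to the FAS–PP difference. The SAP 7 option to repeat analyses when the sets differ by 3 or more patients would not show the loss.

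**4. Size if the rule were applied**

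Plan figures: 35 + 10 = 45 patients (SAP 6) and 4.5 × 52 = 234 infusions (SAP 4.1). Both reproduce.

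The number affected, k, is not given. I assume 0 to 10 of the 35 SCGAM-01 patients, each contributing the maximum 4.5 years:

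- Person-years: PY = (35 − k) × 4.5.
- No SBI, standard Poisson, two-sided 98% interval: upper limit = −ln(0.01)/PY = 4.605/PY.
- One SBI, SAP 8.4 formula: r = 1/PY and ΣCᵢ²/C² = 1, so upper limit = exp(2.33)/PY = 10.278/PY.

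| k | Share of 35 | PY | Upper limit, 0 SBI | Upper limit, 1 SBI |
|---|---|---|---|---|
| 0 | 0% | 157.5 | 0.029 | 0.065 |
| 1 | 2.9% | 153.0 | 0.030 | 0.067 |
| 3 | 8.6% | 144.0 | 0.032 | 0.071 |
| 5 | 14.3% | 135.0 | 0.034 | 0.076 |
| 10 | 28.6% | 112.5 | 0.041 | 0.091 |

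The 4.5 years per patient overstates each loss. The whole study lasts about 4.5 years (protocol 6.2.2), and a rule (a) patient joins after it has begun. Shorter follow-up for everyone would raise all the limits. If each patient gave only 1 year (my assumption), k = 10 would leave 25 PY and limits of 4.605/25 = 0.184 and 10.278/25 = 0.411. These are still below 1.0 per person-year.

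**The case against.** The strongest reply is that nobody would be dropped. SAP 4.1 is a design narrative; the eligibility criteria are the protocol's numbered lists, and a patient who meets them has not violated entry. SAP 4.3 accepts bridging, the SAP refers readers to the protocol for conduct, a panel decides membership, and the FAS is expected to coincide with the safety set. Section 4.1 also still speaks of treatment for up to two years, against about 4.5 years later in the same section, so rule (a) is probably text that was not updated.

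Most of this stands. A reader might infer that the SAP disqualifies every patient who used another IgG between the studies. It does not: rule (b) admits those who finished before the extension started. A reader might also infer that exclusion from the FAS follows automatically. It does not: it needs the panel to treat 4.1(a) as a criterion. That any loss would be systematic, by late-opening sites, is plausible, but the documents give neither site-opening dates nor the number of bridged patients, and the IRB delay is only an example.

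One part does not dispose of the point. The panel decides under a SAP that states a disqualification the protocol lacks and does not say which text governs. An expectation that FAS and safety set will coincide is not a rule that makes them do so.

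**Conclusion.** The conflict is real but confined to patients who completed SCGAM-01 after SCGAM-03 had started and took another commercial SCIG before entry. For them SAP 4.1(a) contradicts protocol v7 and sits uneasily with SAP 4.3. The effect on the FAS and PP sets is conditional on the panel applying the rule.

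The size is unknown because k is not stated. One patient is 1/35 = 2.9% of the SCGAM-01 cohort and contributes fewer than 4.5 person-years. The SBI conclusion would be very unlikely to change: under the assumptions above, with 0 or 1 SBI, every upper limit stays well below 1.0. A reader might take this as a threat to the trial's main result. The documents do not support that, because the primary objective is safety, analysed on a set without an eligibility condition, and all efficacy analysis is descriptive. What is at stake is correct set membership in the secondary analyses, which should be settled before the data review meeting.

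**What to change.** 1. In SAP 4.1, remove the disqualification sentence and the split by completion date, so that the text agrees with protocol 3.2 and 4.1.2. The same-dose condition in rule (b) already matches the protocol and can stay.
2. In SAP 7, state that eligibility for the FAS and PP sets is judged only against the numbered inclusion and exclusion criteria of the protocol that applies to the patient (US or Canadian), not against the SAP's design narrative. Name the protocol version: enrolment began in 2016, v7 dates from October 2018, and the documents do not show whether an earlier version carried rule (a).
3. In the same edit, reconcile the FAS condition. The protocol's Study Outline refers to major eligibility criteria only, while protocol 9.2.1 and SAP 7 refer to all of them.
4. Reconcile the limit on IgG-free time, which is 5 weeks in protocol 4.1.2 but approximately 5 weeks in section 3.2 and in the Study Outline's exclusion criteria. The sponsor must say which applies.

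Items 1 and 2 cost SAP wording only. Items 3 and 4 also need a clarification of the protocol text. None requires new data.

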### 4.2. Age groups

As of protocol version 9 of the predecessor study SCGAM-01, the age ranges for the four age strata were revised to:  $\geq 2$  years and  $< 6$  years,  $\geq 6$  years and  $< 12$  years,  $\geq 12$  years and  $< 17$  years,  $\geq 17$  years and  $\leq 75$  years. In the present extension study, patients will remain in the strata that they were in for analysis in the main study (irrespective of whether their age changed such as to imply a change of age stratum). The maximum patient numbers in each age group will thus be the same as in the main study SCGAM-01. The analyses will reflect these age strata unless the number of patients per stratum is too low for reasonable statistical summaries; if this happens adjacent strata might be combined as indicated by the data.

In addition, and to align the analysis with the results of the SCGAM-01 study, a different definition of age groups (2 to  $< 12$ , 12 to  $< 17$ , 17 to 65, and  $> 65$  years) will be evaluated, and also a comparison of male vs. female subjects will be performed for primary and secondary endpoints.

### **4.3. Selection of Study Population**

The study population consists of patients of both sexes who completed study SCGAM-01. All patients therefore have a confirmed diagnosis of PI and require immunoglobulin replacement therapy due to hypogammaglobulinaemia or agammaglobulinaemia. All patients have been on stable treatment with *octanorm* during the SCGAM-01 study, possibly followed by a comparatively short period of compatible SCIG treatment with another (commercially available) SCIG product.

## 5. Sequence of Planned Analyses

### 5.1. Final Analyses and Reporting

As stated in section 4.1, each patient is treated with *octanorm* over a total period of up to 4.5 years; one week after the last infusion a follow-up visit is performed, and the patient will be switched to a commercially available immunoglobulin product at the discretion of the investigator. Once the last patient has completed the study, data validation will be completed and the database will be locked according to the applicable standard operating procedures. This process includes a data review, the identification and classification of any protocol violations as detailed in section 7, and thus the patient disposition with respect to the analysis populations. All final, planned, analyses identified in the protocol and in this SAP will be performed only after the last patient has completed the study, the subject disposition has been agreed and documented, and the final SAP has been approved.

Key statistics and study results will be made available to the study team following database lock and prior to completion of the final CSR by means of tables, figures and listings.

Any, post-hoc, exploratory analyses completed to support planned study analyses, which were not identified in the final SAP, will be documented and reported in appendices to the CSR. Any results from these unplanned analyses will also be clearly identified in the text of the CSR.

## 6. Sample Size Determination

Approximately 45 patients are planned in total:

- Patients will be taken from the cohort of patients who completed the main study SCGAM-01 in the USA and Canada. The theoretical maximum number of SCGAM-01 patients will be approximately 35 (the expected number in the main study).
- Approximately 10 de novo patients who are under other SCIG treatment, but did not participate in the main study SCGAM-01 are planned in Canada.

No further sample-size considerations apply.

### 6.1. Patient Replacement Policy

Patients withdrawn from the study for any reason will not be replaced.

### 6.2. Premature Termination of the Study

Both, the responsible Investigators and the Sponsor, reserve the right to terminate the study as a whole or centre-wise at any time. Should this be necessary, the procedures will be arranged on an individual study basis after review and consultation by both parties. In terminating the study, the Sponsor and the Investigator will ensure that adequate consideration is given to the protection of the patients' interests. Premature termination will be notified in accordance with applicable regulatory requirements. Please refer to the protocol for further details on premature termination.

## 7. Analysis Populations

The following populations will be considered for the statistical analysis:

The safety analysis set (SAF) consists of all patients who received at least part of one infusion of *octanorm* within this extension study.

The full analysis set (FAS) is defined according to the intention-to-treat principle and consists of all patients of the SAF who satisfy all eligibility criteria and for whom any post screening data in this extension study are available. It is expected that the FAS will coincide with the safety set.

The per-protocol (PP) set consists of all patients of the FAS excluding those with major protocol violations which may have an impact on the analysis of the primary endpoint. This is the set of patients who participated in the study as intended and for whom the primary endpoint can be evaluated as planned.

Only major protocol deviations with the potential to affect the study results significantly or to invalidate the interpretation of the data obtained will lead to exclusion of patients from the PP set; protocol deviations to be considered will include (but will not be limited to):

- Violations of the study entry criteria.
- Administration of any other blood or plasma-derived product or of any other immunoglobulin preparations during the SCGAM-03 study.
- Any prohibited concomitant medication (including long term corticosteroids, daily,  $\geq 0.15$  mg of prednisone or equivalent/kg/day, immunosuppressive and immunomodulatory drugs).
- Failure to attend two scheduled consecutive visits OR three or more scheduled visits during the study for reasons other than clinical reasons.

Analysis of the safety endpoints will be based on the safety set.

Efficacy endpoints will be analysed on basis of the FAS.

Any analysis might be repeated on basis of the PP analysis set if indicated by the data or in case the PP population differs from the FAS by 3 patients or more, to allow for an assessment of the robustness of the results with respect to protocol violations.

The membership of each patient in the respective analysis populations will be determined before the statistical analysis in a data review meeting by a panel consisting of a medical expert from the Sponsor, the clinical study manager, the data manager and the study statistician.

All protocol violations documented during the conduct of the study or identified at the data review process prior to DB lock will be reviewed and classified as minor or major and with respect to its effect on the planned analysis. Only major protocol violations with the potential to significantly affect the study results or to invalidate the interpretation of the data obtained will lead to exclusion of patients from the PP set. This classification of protocol violations is the joint responsibility of the clinical study manager, the study statistician, and Octapharma's responsible medical expert, and will be performed and documented before the database is locked and the statistical analyses are performed.

